9 STUDY CALENDAR

Required Studies	Screening ª	Baseline ^b	Weeks 1, 2, 3 (+/- 2 days) ^c	Weeks 4, 6 (+/- 2 days) ^c	Week 8 (-2, +7 days) ^c	Week 12 (+/- 2 days) ^c	Week 15 (-2, +7 days) ^{c, j}	Off Study (if prior to week 15) ^d
Informed consent	Х							
Medical History	Х							
Performance status ^m	Х							
Study visits ⁱ	Xd	Х			Х		Х	Х
Study coordinator phone calls ^{k, n}			Х	Х	Х	X	XI	XI
Vital signs ^e	Х							
Concomitant medications	Х	Х						
Adverse event assessment			Х		Х		Х	Х
Patient reported questionnaires ^f								
- BPI	Х	Х	Х	Х	Х	Х	Х	Х
- PROMIS		Х		X (wk 4 only)	Х		Х	Х
- GRC			X°	X (wk 4 only)	Х	Х	Х	Х
- METE		Х						
- FM Survey		Х					Х	Х
- CSQ		Х					Х	Х
- PANAS		Х					Х	Х
- PHQ9 ^p	Х	Х						
Phlebotomy ^g								
- Research	X ^r X				X X		Х	X X
 Clinical labs (aspartate aminotransferase, alanine aminotransferase, total 	X			X (wk 4 only)	Х		X	X
bilirubin, serum creatinine, complete blood count)								
Al therapy (standard of care)								•
Dispense study medicine		Х			Х			
CBD treatment ^h								
Medication log		Х			Х		Xi	Xi

a. Screening and baseline visits can take place on the same day. The informed consent can be completed either in person or remotely using SignNow. The BPI and PHQ9 will be completed after signing the ICF and can be completed by phone or electronically. Screening clinical lab studies must be completed within 28 days of registration; if they have already been completed for another reason (other than participating in this clinical trial) they do not need to be repeated.

b. Baseline visit can take place up to 4 weeks after the screening visit. Patient does not need to be seen by physician or advanced practice provider.

c. Timed based on initiation of CBD therapy.

d. This is the visit conducted at the time of AI discontinuation and/or study drug discontinuation as per section 7.3.1. These questionnaires should be completed within 3 business days of medication discontinuation. Patients will return remaining study drug and medication log at that study visit or at their next routine clinic

visit. Also if a patient discontinues study drug early, she should continue to complete questionnaires according to the study calendar through the 15 week timepoint.

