k. Study coordinator calls are to assess adverse events including suicidality and (if applicable) determine if there is a reason that the patient should not increase the dose by one dose level (as per section 8.1.1). If there is a question about whether the patient should or should not increase the dose, the study coordinator will contact the PI or Co-I. Also if patients have not completed questionnaires or if they decline to complete questionnaires electronically, the study coordinator should ask the questions by phone.

I. The study coordinator should follow-up with the patient by phone 30 days following the off-study visit to assess resolution of any AEs as per section 16.5. m. Performance status assessment at screening will be performed by a licensed physician (or physician's assistant or nurse practitioner) or registered nurse. Can have been performed up to 28 days before the screening visit, and can be performed during a virtual visit.

n. The study coordinator will ask about suicidal ideation on the phone calls using question 9 from the PHQ9: "How often have you been bothered by the following in the past week: Thoughts that you would be better off dead, or thoughts of hurting yourself in some way? Not at all, several days, more than half the days, nearly every day". If a patient reports anything other than "Not at all" to the question, the patient's oncology treatment team will be notified and the patient will be managed according to usual clinical protocols. If the treatment team is not available, the PI or another of the co-Is will be notified.

o. GRC should be completed at week 2.

p. The study coordinator should review the response to PHQ9 question 9 prior to dispensing the study medication to the patient. If the answer to the question is anything other than "Not at all", the study medication should not be dispensed and the patient's clinical team or covering provider should be notified immediately.

q. The screening study visit can be conducted virtually if the necessary patient information (other than lab results) can be found in the medical chart. Patient will need to undergo phlebotomy prior to enrollment in the study if screening lab studies have not otherwise been performed within the past 28 days.

r. If clinical lab studies do not need to be performed at screening because they have been performed within the 28 day window, the research blood specimens at screening can instead be collected at baseline.

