10.2 Patient-Reported Outcomes

The validated instruments used in this study are as follows:

Brief Pain Inventory (BPI): The BPI is a 17-item patient self-rating scale that assesses sensory and reactive components of pain.³⁸ For sensory components, it addresses severity, location, chronicity, and degree of relief due to therapy. For reactive components, it assesses depression, suffering, and perceived availability of relief. Reliability has been demonstrated over short intervals using test retest item correlation; worst pain, r=0.93, usual pain, r=0.78, pain now r=0.59. It has been validated in patients with both cancer and non-cancer pain.^{46, 47} Ratings of pain interference with various activities increased as ratings of pain severity were higher. The proportion of patients receiving opioid analgesics also increased with increased severity rating.

The BPI uses 0 to 10 numeric rating scales for item rating because of its simplicity and lack of ambiguity. Since pain can be variable over a day, the BPI asks patients to rate their pain at the time of completing the questionnaire, and also at its worst, least, and average over the previous 7 days. The primary endpoint for this clinical trial will be based on the 7-day worst joint pain and/or myalgias as reported on the BPI. The ratings can be combined to give a composite index of pain severity. Also, using numeric 0 to 10 scales, with 0 being "no interference" and 10 being "interferes completely", the BPI asks for ratings of the degree to which pain interferes with mood, walking and other physical activity, works, social activity, relations with others, and sleep. The mean of these scores can be used as a pain interference score. This will be completed at each timepoint.

PROMIS-29+2 Profile v2.1: A validated questionnaire that assesses patient-reported symptoms over the past 7 days in 9 PROMIS domains (fatigue, sleep disturbance, physical functioning, depression, anxiety, ability to participate in social roles and activities, cognitive function-abilities, and pain intensity and interference). Raw scores for each domain are calculated and then converted to a T-score, with a mean of 50 and a standard deviation of 10. Higher T scores represent more of the concept being measured.³⁹ Pain severity and interference will be excluded since overlaps with BPI. This 26-item questionnaire will be completed at baseline, 4, 8, and 15 weeks (and off study if patient discontinues before week 15).

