16.5.2 Adverse Event Reporting Requirements

Adverse event (AE) monitoring and reporting is a routine part of every clinical trial and is done to ensure the safety of subjects enrolled in the studies as well as those who will enroll in future studies using similar agents. Data on adverse events will be collected from the time of the initial study treatment through 30 days after the last dose of study treatment. Any serious adverse event that occurs more than 30 days after the last study treatment and is considered related to the study treatment must also be reported. Serious Adverse Events (SAEs) will continue to be followed until:

- Resolution or the symptoms or signs that constitute the serious adverse event return to baseline;
- There is satisfactory explanation other than the study treatment for the changes observed; or
- Death.

The investigator is responsible for the detection, documentation, grading and assignment of attribution of events meeting the criteria and definition of an AE or SAE. The definitions of AEs and SAEs are given below. It is the responsibility of the principal investigator to ensure that all staff involved in the trial is familiar with the content of this section.

Any medical condition or laboratory abnormality with an onset date before initial study treatment administration is considered to be pre-existing in nature. Any known pre-existing conditions that are ongoing at time of study entry should be considered medical history.

All events meeting the criteria and definition of an AE or SAE, as defined in Section 8.3, occurring from the initial study treatment administration through 30 days following the last dose of the study treatment must be recorded as an adverse event in the patient's source documents and on the CRF regardless of frequency, severity (grade) or assessed relationship to the study treatment.

In addition to new events, any increase in the frequency or severity (i.e., toxicity grade) of a pre-existing condition that occurs after the patient begins study treatment is also considered an adverse event.

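### The scripted suicidality item asks only about the past week, while coordinator calls after week 4 are 2 to 4 weeks apart; at nominal timing it does not ask about 49 of 105 treatment days

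*Combined protocol and SAP*

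**What the plan says.** All of the following is in the Combined protocol and SAP.

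- **Call schedule.** The Study Calendar row "Study coordinator phone calls" is marked at weeks 1, 2, 3, 4, 6, 8, 12 and 15 and at an early off-study visit. Footnote c counts these times from the start of CBD.
- **Purpose of the calls.** Footnote k: "Study coordinator calls are to assess adverse events including suicidality". It sets no look-back period and gives no question.
- **The question.** Footnote n supplies it: PHQ-9 item 9, opening "How often have you been bothered by the following in the past week". The answers run from *not at all* through *several days* upward.
- **The action.** For any answer other than the lowest, footnote n says the patient's "oncology treatment team will be notified and the patient will be managed according to usual clinical protocols".
- **Last call.** The week 15 and off-study call marks also carry footnote l: "The study coordinator should follow-up with the patient by phone 30 days following the off-study visit to assess resolution of any AEs".
- **Adverse events generally.** Section 16.5.2: "Data on adverse events will be collected from the time of the initial study treatment through 30 days after the last dose".
- **Other instruments.** The PHQ-9 is marked only at screening and baseline. PROMIS is given at baseline, weeks 4, 8 and 15, and off study if early; section 10.2 describes it as "A validated questionnaire that assesses patient-reported symptoms over the past 7 days in 9 PROMIS domains". Under section 15.1, patients are told that their provider does not see questionnaire answers.

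**The concern.** The recall period and the call interval agree up to week 4 and then part. From the week 6 call on, a patient who had suicidal thoughts ten days earlier and none since can truthfully give the lowest answer, and footnote n then prompts nothing.

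By the protocol's own standard any ideation matters. A history of it excludes a patient (5.2.5), a positive item 9 stops dispensing (footnote p), and any positive answer on a call leads to notification (footnote n). An episode that came and went between calls may still be something the treatment team should know about, yet the one scripted question does not ask for it, and neither the PHQ-9 nor PROMIS fills the interval.

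What is at stake is completeness of safety ascertainment. Section 12.3 does not analyse the item, so no efficacy result is touched.

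**Working it through.** The plan states no coverage figure, so there is none to reproduce. The check is a day count.

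**Inputs.** Treatment lasts 15 weeks (7.3), taken as 105 days. Calls fall on nominal days 7, 14, 21, 28, 42, 56, 84 and 105 (calendar, footnote c). Recall is 7 days (footnote n), taken as the 7 days ending on the call day. Call windows (calendar) are ±2 days for weeks 1 to 4, 6 and 12, and −2/+7 days for weeks 8 and 15.

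**Nominal timing.** Unasked days before each call = interval since the previous call (or since the start of CBD) − 7.

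| Call (week) | Interval (days) | Unasked | Which days |
|---|---|---|---|
| 1, 2, 3, 4 | 7 each | 0 | none |
| 6 | 14 | 7 | 29–35 |
| 8 | 14 | 7 | 43–49 |
| 12 | 28 | 21 | 57–77 |
| 15 | 21 | 14 | 85–98 |

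Total: 7 + 7 + 21 + 14 = 49 of 105 days (47%), or 7 of 15 weeks. The longest run is 21 days.

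**Call windows.** Over all in-window call patterns, with treatment fixed at 105 days, the total is 49 to 64 days.

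- Minimum: eight calls of 7 days cover at most 56 days, and 105 − 56 = 49. No use of the windows can improve on the nominal figure.
- Maximum, for example calls on days 9, 12, 23, 26, 40, 54, 82 and 112: days covered are 7 + 3 + 7 + 3 + 7 + 7 + 7 + 0 = 41, and 105 − 41 = 64.
- The stretch between the week 8 and week 12 calls runs from 82 − 63 − 7 = 12 to 86 − 54 − 7 = 25 days.

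**Other reading of footnote l.** If the week 15 mark means only a call 30 days after the visit, seven calls remain: 105 − 7 × 7 = 56 days (53%) nominally, and 56 to 64 across windows.

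**Illustration for short episodes.** Assume, without support in the documents, that an episode of L days is equally likely to start on any day and ends within treatment, and that nobody reports it under footnote k. The share lying wholly outside the recall is the number of start days with all L days unasked, divided by (105 − L + 1).

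| L (days) | Nominal call days | Largest share across windows |
|---|---|---|
| 3 | 41/103 = 40% | 52/103 = 50% |
| 7 | 25/99 = 25% | 37/99 = 37% |
| 14 | 9/92 = 10% | 18/92 = 20% |
| 21 | 1/85 = 1% | 5/85 = 6% |

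The nominal shares are not upper bounds, since calls within their windows can exceed them. The documents give no ideation rate, so no number of missed episodes follows.

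**The case against.** The strongest reply is that suicidality is already covered. Footnote k puts it on the agenda of every call with no look-back limit, and section 16.5.2 requires adverse events to be recorded from first dose to 30 days after the last, whatever their grade or frequency. An episode reported that way enters the adverse event pathway: grading and attribution by the investigator, the dose table in 8.1.1 where related, and notice to the principal investigator if serious. This stands, and it limits the point. A reader might infer from 49 of 105 days that suicidality goes unmonitored for nearly half of treatment. The documents do not support that: only the scripted item, and the notification tied to it, has the short reach.

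What survives is that footnote k gives no question and no action specific to suicidality. For an episode outside the past week, the plan relies on the patient raising it in general adverse event questioning.

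It can also be said that a recent-recall item aimed at current risk is a legitimate choice, that weekly calls cover the titration weeks (7.1.2), and that ideation which persists, or occurred in the week before a call, is caught. All true. Wider recall would not bring detection forward; it would add reports of episodes already over. It would also lose recency if nothing replaced it, and the fix must deal with that.

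The calendar's "Adverse event assessment" row, as extracted, has no mark at weeks 4, 6 or 12. That table is visibly damaged in extraction and footnote k says in prose that the calls assess adverse events, so nothing here rests on those blanks.

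**Conclusion.** The point holds as a minor mismatch between a one-week recall and calls 2 to 4 weeks apart. The scripted item does not ask about 49 of 105 treatment days at nominal timing, 49 to 64 across the call windows, and 56 nominally if the week 15 call takes place only 30 days after the visit. The consequence is confined to short episodes that resolve more than a week before a call and are not otherwise reported.

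This assumes 105 days of treatment, all calls made within their windows, and a literal 7-day reading of the item. The day counts follow from the calendar; the episode shares are illustration only.

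A reader might also infer a dose-related hazard, because the unasked days all fall after week 4, when patients who tolerate titration are on the top dose. Nothing in the documents supports a claim of dose-related suicidality, and none is made here.

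**What to change.** Keep the call schedule and the item. In footnote n and the call script:

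1. Replace the past-week recall with *since our last call* at every call, including the off-study call and any 30-day call under footnote l. At week 1, use *since starting the study drug*.
2. State that any occurrence, even a single one, counts as an answer other than *not at all*, because the lowest positive option is *several days*.
3. For any positive answer, have the coordinator record when it last occurred, within the past week or earlier, so that urgency stays visible.

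This leaves no unasked days up to the last call for any in-window pattern. If the week 15 call falls on day 103 and treatment runs to day 105, the last 2 days are reached only by the 30-day call. Two lighter changes do less:

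- A 14-day recall would still leave 14 + 7 = 21 days unasked at nominal timing.
- Changing only the calls at weeks 6, 8, 12 and 15 could leave 8 days: calls on days 5, 16, 19 and 30 miss days 6–9 and 20–23.

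The cost is a few lines of text and no extra calls. Frequency answers become less comparable between calls because the intervals differ, which matters little when any positive answer triggers action. Some notifications will concern resolved episodes, in a number the documents do not allow one to estimate, and each positive answer needs a brief follow-up on recency. No analysis in section 12.3 changes.

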10 STUDY PROCEDURES

10.1 Screening Evaluations

A review of inclusion/exclusion criteria will be conducted to determine the patient's eligibility for enrollment. Study procedures will be reviewed with the patient, and documentation of informed consent will be obtained. After signing the informed consent form (ICF) either in person or electronically using SignNow or other process approved by the UM IRBMED, patients will be assigned a unique study ID number in sequential order. Patients will complete the BPI and PHQ9 questionnaires after signing the ICF in order to confirm eligibility. Those who are found to be ineligible will be replaced.

The following medical history elements will be abstracted from the medical record: date of breast cancer diagnosis, tumor information (e.g., tumor histology, receptor status), treatment information (e.g., surgery type and dates, chemotherapy doses and dates, radiation therapy doses and dates), information about other relevant medical co-morbidities and concomitant medications (as outlined on the case report form). The patient's email address and phone number will also be recorded.

10.2 Patient-Reported Outcomes

The validated instruments used in this study are as follows:

Brief Pain Inventory (BPI): The BPI is a 17-item patient self-rating scale that assesses sensory and reactive components of pain.³⁸ For sensory components, it addresses severity, location, chronicity, and degree of relief due to therapy. For reactive components, it assesses depression, suffering, and perceived availability of relief. Reliability has been demonstrated over short intervals using test retest item correlation; worst pain, r=0.93, usual pain, r=0.78, pain now r=0.59. It has been validated in patients with both cancer and non-cancer pain.^{46, 47} Ratings of pain interference with various activities increased as ratings of pain severity were higher. The proportion of patients receiving opioid analgesics also increased with increased severity rating.

The BPI uses 0 to 10 numeric rating scales for item rating because of its simplicity and lack of ambiguity. Since pain can be variable over a day, the BPI asks patients to rate their pain at the time of completing the questionnaire, and also at its worst, least, and average over the previous 7 days. The primary endpoint for this clinical trial will be based on the 7-day worst joint pain and/or myalgias as reported on the BPI. The ratings can be combined to give a composite index of pain severity. Also, using numeric 0 to 10 scales, with 0 being "no interference" and 10 being "interferes completely", the BPI asks for ratings of the degree to which pain interferes with mood, walking and other physical activity, works, social activity, relations with others, and sleep. The mean of these scores can be used as a pain interference score. This will be completed at each timepoint.

PROMIS-29+2 Profile v2.1: A validated questionnaire that assesses patient-reported symptoms over the past 7 days in 9 PROMIS domains (fatigue, sleep disturbance, physical functioning, depression, anxiety, ability to participate in social roles and activities, cognitive function-abilities, and pain intensity and interference). Raw scores for each domain are calculated and then converted to a T-score, with a mean of 50 and a standard deviation of 10. Higher T scores represent more of the concept being measured.³⁹ Pain severity and interference will be excluded since overlaps with BPI. This 26-item questionnaire will be completed at baseline, 4, 8, and 15 weeks (and off study if patient discontinues before week 15).

11 CRITERIA FOR EVALUATION AND ENDPOINT

11.1 Safety

Routine safety and tolerability will be evaluated from the results of reported signs and symptoms and the laboratory studies (LFTs, creatinine, hemoglobin). More frequent safety evaluations may be performed if clinically indicated or at the discretion of the investigator.

11.2 Stopping Rules

N/A

12 STATISTICAL CONSIDERATIONS

12.1 Statistical hypothesis

Use of CBD in postmenopausal women with breast cancer who are experiencing AIMSS will result in improvement in joint pain and stiffness. As a secondary hypothesis, use of CBD will result in improvement in anxiety.

12.2 Sample size determination

The primary endpoint of this study is the absolute change in worst pain from baseline to 15 weeks with CBD. Analysis will be based on intention-to-treat, and all patients who complete the 15 week assessment with BPI will be evaluable for the primary endpoint. There are no available prior data on symptom response in patients with AIMSS treated with CBD. Therefore, the statistical plan for this study was based on data from other studies of patients with AIMSS. Based on prior data from acupuncture therapy for treatment of AIMSS, we expect a baseline worst pain score of 6.5 and standard deviation of 3. Therefore, with a sample size of 40 evaluable patients, a two-sided type I error of 5%, we can detect a standardized effect size of 0.45 or a change in worst pain of 1.4 points with 80% power. Based on IMMPACT guidelines, a 2-point reduction in pain is considered to be clinically meaningful for an individual patient.⁵⁷ We power to find a slightly smaller effect size based on potentially more heterogeneity in our sample (i.e. higher variability). To account for anticipated treatment discontinuation rates of 10%, we will need an additional 4 patients (for 40 completing patients).

An increased sample size of 44 patients and a longer duration of therapy (15 weeks) were chosen to allow for precise evaluation of the efficacy of CBD and to expand our ability to perform and interpret the correlative studies. Further, the funder of this study voiced concern that a smaller sample size (of 20 patients) and a shorter treatment duration (8 weeks) were insufficient to evaluate the primary endpoints of this study.

